19.0 Risks to Subjects

19.1 In your opinion, what is the overall risk (physical and nonphysical) to research subjects in this study (minimal, greater than minimal or unknown)

The risks of this study are minimal.

Repetitive Transcranial Magnetic Stimulation (rTMS) is delivered using a Class II FDA device that is approved for the treatment of depression. The device is currently being investigated for use in other disorders, including headaches, Obsessive-Compulsive Disorder, and as a method to treat pain. There have been three review articles written on the safe clinical use of rTMS.¹⁻³ The most recent article was published in 2021 and classified the risks of rTMS as “very low”.² The most common side effects of rTMS are headaches and local pain around the stimulation site. These side effects are transient and usually mild.¹ The most concerning potential adverse event is the induction of a seizure. There have been 41 reported cases of seizures that may have been induced by rTMS.^{2,4} The majority of these seizures occurred before the publication of the 1998 safety guidelines.^{2,3} Thirteen of the seizures occurred in healthy individuals and 28 occurred in patients with a psychiatric or neurologic condition. Fifty four percent of the reported seizures were classified as general and 27% were focal to bilateral tonic-clonic.⁴

The overall risk of seizure with rTMS is difficult to calculate because the number of total exposures is unclear. Lerner et. al surveyed 174 laboratories and clinics that utilize rTMS in research or in clinical care.⁵ The respondents reported 24 seizures over an estimated 318,560 TMS sessions (.08/1000). TMS sessions that followed the parameters described in the 2009 guidelines¹ and included only low risk patients resulted in a seizure risk of <.02/1000 sessions (1 seizure per 60,000 sessions). Subjects with elevated seizure risk treated with rTMS following the guidelines had a .33/1000 risk of seizure.

Several factors that have the potential to increase the risk of seizures with rTMS have been identified. Due to the very low incidents of seizures, it is difficult to confidently know if and how much these factors increase the risk of seizure. Authors have also erred on the side of overestimation by setting a low bar for associating TMS with the seizure.^{2,5} It is likely that several of the reported seizures were convulsive syncopal episodes or seizures that were unrelated to the TMS. One of the most accepted risk factors for TMS induced seizure is a history of epilepsy.² In the Lerner study, 29% (7/24) of the seizure cases were in patients with a history of epilepsy. Cases of seizure also occurred in individuals with a history of stroke (5), psychiatric disorders treated with medications that lower the seizure threshold (3), tumors (2), and arteriovenous malformation (1).⁵ Four seizures (17%) occurred in individuals without any identifiable risk factors.⁵ Although seizure is a serious risk factor, there have been no reports of long-term deleterious effects in those individuals who had a seizure that was attributed to rTMS.

Based on this information we agree with Rossi et al that treatment with a Transcranial Magnetic Stimulator is low risk.¹ To further reduce the risk of adverse events we will follow the accepted stimulation and monitoring guidelines.^{2,6} Stimulation parameters will be at intensities below motor evoked potential, we will provide adequate time between stimulation trains, and we will monitor for increasing EMG activity in contralateral muscles.⁶ We will exclude subjects who are epileptic and who have implanted metal or electronic devices in or near their head, such as aneurism clips, stents, pacemakers, cochlear implants, implanted brain stimulators, and ocular implants. The research team will have an emergency plan in place to deal with any adverse events. Subjects receiving rTMS will be placed in a safe position that will reduce the risk of

injury if a seizure occurs. If a serious adverse event, such as a seizure occurs, the research team will call EMS services and encourage the subject to seek immediate emergency care. Subjects will be made aware of the potential adverse events during the informed consent process.

interventions during the 4 week intervention period of the trial. The follow-up data collection survey will ask participants to report any changes or additions to their management strategies.

19.3 List the reasonably foreseeable risks, discomforts, hazards, or inconveniences to the subjects related to their participation in the research. Consider physical, psychological, social, legal, and economic risks. Include a description of the probability, magnitude, duration, and reversibility of the risks.

NOTE: Breach of confidentiality is always a risk for identifiable subject data.

There have been three review articles written on the safe clinical use of rTMS.¹⁻³ The most recent article was published in 2021 and classified the risks of rTMS as “very low”.² The most common side effects of rTMS are headaches and local pain around the stimulation site. These side effects are transient and usually mild.¹ The most concerning potential adverse event is the induction of a seizure. There have been 41 reported cases of seizures that may have been induced by rTMS over the past three decades since the introduction of rTMS.^{2,4} The majority of these seizures occurred before the publication of the 1998 safety guidelines.^{2,3} Thirteen of the seizures occurred in healthy individuals and 28 occurred in patients with a psychiatric or neurologic condition. Fifty-four percent of the reported seizures were classified as general and 27% were focal to bilateral tonic-clonic.⁴

The overall risk of seizure with rTMS is difficult to calculate because the number of total exposures is unclear. Lerner et. al surveyed 174 laboratories and clinics that utilize rTMS in research or in clinical care.⁵ The respondents reported 24 seizures over an estimated 318,560 TMS sessions (.08/1000). TMS sessions that followed the parameters described in the 2009 guidelines¹ and included only low risk patients resulted in a seizure risk of <.02/1000 sessions (1 seizure per 60,000 sessions). Subjects with elevated seizure risk treated with rTMS following the guidelines had a .33/1000 risk of seizure.

Several factors that have the potential to increase the risk of seizures with rTMS have been identified. Due to the very low incidents of seizures, it is difficult to confidently know if and how these factors increase the risk of seizure. Authors have also erred on the side of overestimation by setting a low bar for associating TMS with a seizure.^{2,5} Several of the reported seizures were likely convulsive syncopal episodes or seizures that were unrelated to the TMS. One of the most accepted risk factors for TMS induced seizure is a history of epilepsy.² In the Lerner study, 29% (7/24) of the seizure cases were in patients with a history of epilepsy. Cases of seizure also occurred in individuals with a history of stroke (5), psychiatric disorders treated with medications that lower the seizure threshold (3), tumors (2), and arteriovenous malformation (1).⁵ Four seizures (17%) occurred in individuals without any identifiable risk factors.⁵ Although seizure is a serious risk factor, there have been no reports of long-term deleterious effects in those individuals who had a seizure that was attributed to TMS.

Based on this information we agree with Rossi et al that treatment with a Transcranial Magnetic Stimulator is low risk.¹ To further reduce the risk of adverse events we will follow the accepted stimulation and monitoring guidelines.^{2,6} Stimulation parameters will be at intensities below motor evoked potential, we will provide adequate time between stimulation trains, and we will monitor for increasing EMG activity in contralateral muscles.⁶ We will also exclude subjects who are epileptic, with a family history of epilepsy in immediate blood relatives, pregnant, and

who have implanted metal or electronic devices in or near their head, such as aneurism clips, stents, pacemakers, cochlear implants, implanted brain stimulators, and ocular implants. The research team will have an emergency plan in place to deal with any adverse events. Subjects receiving rTMS will be placed in a safe position that will reduce the risk of injury if a seizure occurs. If a serious adverse event, such as a seizure occurs, the research team will call EMS services and encourage the subject to seek immediate emergency care. Subjects will be made aware of the potential adverse events during the informed consent process.

No significant adverse events have been reported for the rehabilitation procedures that will be used in this study. The procedures will be administered by licensed physical therapists with experience treating patients with CRPS. The procedures used during the rehabilitation sessions is standardized but will be tailored to the individual subject's tolerance.

Subjects will also be informed that study personnel will not be responsible for the medical costs incurred as a result of an adverse event.

3. Wassermann EM. Risk and safety of repetitive transcranial magnetic stimulation: report and suggested guidelines from the International Workshop on the Safety of Repetitive Transcranial Magnetic Stimulation, June 5-7, 1996. *Electroencephalogr Clin Neurophysiol.* 1998;108(1):1-16. doi:10.1016/S0168-5597(97)00096-8
4. Chou Y hui, Ton That V, Chen AYC, Sundman M, Huang YZ. TMS-induced seizure cases stratified by population, stimulation protocol, and stimulation site: A systematic literature search. *Clin Neurophysiol.* 2020;131(5):1019-1020. doi:10.1016/J.CLINPH.2020.02.008
6. Repetitive Transcranial Magnetic Stimulation (rTMS) Systems - Class II Special Controls Guidance for Industry and FDA Staff | FDA. US Food and Drug Administration Guidance Documents. Published 2011. Accessed November 23, 2021. <https://www.fda.gov/medical-devices/guidance-documents-medical-devices-and-radiation-emitting-products/repetitive-transcranial-magnetic-stimulation-rtms-systems-class-ii-special-controls-guidance>

19.4 Describe procedures performed to minimize the probability or magnitude of risks, including procedures being performed to monitor subjects for safety.

Subjects will be screened for risk factors that may increase the chances of an adverse event using a standard form. The treatment protocols and inclusion/exclusion criterion have been developed based on the most up-to-date safety guidelines. Safety and monitoring procedures, as described above, will be implemented at all times during the treatment sessions.

19.5 If applicable, indicate which procedures may have risks to the subjects that are currently unforeseeable.

N/A

19.6 Indicate which research procedures, if any, may have risks to an embryo or fetus should the subject be or become pregnant.

N/A

19.7 If you responded to 19.6 that there are such risks, how will you minimize the risk of a pregnancy occurring during the course of the study? (Select all that apply)

- Counseling on birth control and /or abstinence
- Pregnancy test during the study
- Pregnancy test prior to initiation of the study
- Other _____
- N/A

19.8 If applicable, describe possible risks to others who are not subjects.

N/A

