7.0 Inclusion and Exclusion Criteria

7.1 Describe, in bullet points, the criteria that define who will be included in this study:

Eligible subjects will meet all of the following criteria:

- 1) 18 years or older
- 2) Upper or lower extremity CRPS Type 1 (also called RSD-Reflex Sympathetic Dystrophy) of at least 6 months. It is anticipated that most potential subjects will have an established diagnosis of CRPS by a healthcare provider. Study members will confirm the diagnosis by using the Budapest Criteria, which is the most current diagnostic criterion for CRPS.
 - a. Budapest Criteria- To be diagnosed with CRPS individuals must have continued pain, which is disproportionate to inciting event, no other diagnosis that better explains the symptoms and 1 symptom in 3 of the 4 categories and 1 sign in 2 of the 4 categories below.
 - i. Sensor-hyperalgesia and/or allodynia
 - ii. Vasomotor-temperature asymmetry, skin color changes or asymmetry
 - iii. Sudomotor/Edema-Edema and/or sweating changes and/or sweating asymmetry
 - iv. Motor/trophic-reduced ROM, weakness, tremor, dystonia, or changes in hair, nail, or skin.
- 3) Pain rating on NPRS of at least 4/10
- 4) No initiation of a new intervention (i.e., medication, rehab, injections) in the previous 2 months.

- 5) No plan to initiate a new intervention during the study treatment timeframe (4 weeks).

7.2 Describe, in bullet points, the criteria that define who will be excluded from this study:

Potential subjects with any of the following will be excluded.

- 1) A history of seizures or epilepsy
- 2) Intracranial metallic devices
- 3) Pacemaker
- 4) Intrathecal infusion pumps
- 5) Brain or spinal cord stimulators with epidural electrodes
- 6) Other ferromagnetic metallic intracranial implants
- 7) Apparent mental or psychiatric disorder that prevents adequate informed consent
- 8) Current pregnancy
- 9) Non-English speaking

7.3 Indicate whether you are specifically recruiting or targeting any of the following special populations in your study using the checkboxes below.

N/A

- Adults unable to consent (*complete and upload Supplemental Form A*)
- Minors (under 18 years old)
- Pregnant women
- Prisoners

6.4 Indicate if you will include minorities (American Indians, Alaskan Native, Asian, Native Hawaiian, Pacific Islander, Black [not of Hispanic origin] and Hispanic) as Federal mandates require that you include minorities unless you can justify their exclusion

- Yes
- No, Justify:

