17.5 Describe the frequency of safety data collection, including when safety data collection starts.

Safety data will be collected at every treatment session. This will occur before (to assess response to previous sessions), during, and after each treatment session.

17.6 Describe who will review the safety data.

The primary investigator and any study personnel involved in treatment delivery. If these individuals have concerns, they will discuss the safety data with the entire research team.

17.7 Describe the frequency of review of cumulative safety data.

Normal and expected mild adverse events will be dealt with by the treating provider and reported to the PI, as they occur. All events requiring subjects to stop a treatment will be discussed with the entire research team. The study team will have meetings at least every 3 months to discuss any safety concerns.

17.8 Describe the statistical tests for analyzing the safety data to determine whether harm is occurring.

Not applicable. Safety data will be monitored onsite by investigators.

17.9 Describe any conditions that trigger an immediate suspension of the research.

A seizure occurring in one of the participants.

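### Sections 7.2, 19.1 and 19.3 state different exclusion lists, so a person whom 19.3 describes as excluded can satisfy every written eligibility criterion

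*Combined protocol and SAP*

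**What the plan says.** Section 7.2 is the formal exclusion list. It opens with "Potential subjects with any of the following will be excluded" and gives nine items. Its only seizure item is "A history of seizures or epilepsy". Its general implant items are "Intracranial metallic devices" and "Other ferromagnetic metallic intracranial implants". It also lists pacemakers, intrathecal infusion pumps, "Brain or spinal cord stimulators with epidural electrodes" and current pregnancy. It does not point to further exclusions elsewhere.

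Section 19.1, on overall risk, states: "We will exclude subjects who are epileptic and who have implanted metal or electronic devices in or near their head". Its examples are aneurysm clips, stents, pacemakers, cochlear implants, brain stimulators and ocular implants.

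Section 19.3, on foreseeable risks, repeats most of 19.1, including the same implant examples. It adds pregnancy and subjects "with a family history of epilepsy in immediate blood relatives".

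Section 9.1 invites people who meet the eligibility criteria, after phone screening with a standardized document and a TMS questionnaire. The questionnaire is repeated on arrival, and section 11.0 lists TMS screening at each later session. Section 19.4 mentions a standard form for risk factors.

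**The concern.** Eligibility should have one answer for any given person. Here it depends on which section is read. An investigator working from 7.1 and 7.2 could find a person eligible whom 19.3, in the same submission to the ethics board, says will not take part.

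The items that differ are safety exclusions for brain stimulation, and they bear on both arms: section 11.0 gives sham subjects the same localization stimulation before the sham procedure. Section 17.9 makes "A seizure occurring in one of the participants" a trigger for immediate suspension, so the protocol itself treats seizure-related eligibility as serious. The mismatch also means that a screening form cannot be checked against the protocol, because there is no single list to check it against.

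**Working it through.** The protocol gives no figure on this point, so the check is a comparison of the three lists, item by item.

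| Item | 7.2 | 19.1 | 19.3 |
|---|---|---|---|
| Own epilepsy | Excluded | Excluded | Excluded |
| Own past seizure without epilepsy | Excluded | Not named | Not named |
| Epilepsy in an immediate relative | Not named | Not named | Excluded |
| Pregnancy | Excluded | Not named | Excluded |
| General implant scope | Intracranial, metallic | Metal or electronic, in the head or close to it | Same as 19.1 |
| Ocular implants | Not named; not intracranial on a plain reading | Named | Named |
| Cochlear implants | Not named; arguably within intracranial metal | Named | Named |
| Stents | Covered if intracranial and metallic; otherwise not | Named | Named |
| Aneurysm clips | Covered as intracranial metal | Named | Named |
| Pacemakers | Named | Named | Named |
| Brain stimulators | Named, with epidural electrodes | Named | Named |
| Spinal cord stimulators with epidural electrodes | Named | Not named | Not named |
| Intrathecal pumps | Named | Not named | Not named |

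**Family history.** Section 19.3 names being epileptic and having an epileptic relative as separate grounds. The protocol therefore treats them as distinct, and the seizure item in 7.2 cannot fairly be stretched to cover relatives. Take an adult with eligible CRPS, an epileptic parent, no seizures of their own and none of the other listed exclusions. Every item of 7.1 and 7.2 is satisfied, and 19.3 says this person is excluded. That case alone establishes the contradiction. Section 19.1 also lacks the item, so the two risk passages disagree with each other.

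**Implants.** Section 19 is wider than the general items in 7.2 in two respects: location (close to the head, not only inside the skull) and type (electronic as well as metal). Ocular implants and devices near but outside the skull fall in the gap. For stents and cochlear implants the gap is partial.

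**Direction.** Section 19.3 contains everything in 19.1, but 7.2 and 19.3 each name items that the other does not. Staff cannot resolve the conflict by picking the longest list.

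**Screening text.** Sections 9.1, 11.0 and 19.4 describe a questionnaire and forms. Their items are not in the document, and no sentence says that a positive answer excludes. They neither close the gap nor show that it stays open in practice.

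**The case against.** The strongest reply is that screening is layered. The TMS questionnaire is used by phone, on arrival and at later sessions, and a standard risk-factor form is mentioned as well. These may well ask about relatives and about any implant near the head. This stands in part: actual enrolment of such a person is not shown, and the absence of the forms from the document is not a fault in the plan. It does not remove the conflict in the protocol text.

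A second reply is that the section 19 implants are only examples and that some are already in 7.2. This also stands in part. An intracranial metallic stent falls under 7.2, and a cochlear implant arguably does. Describing stents and cochlear implants as simply missing would go too far; the difference is one of scope.

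A reader might also infer more than the document supports:

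- **A seizure risk.** Section 19 quotes under .02 per 1000 sessions for low-risk patients and .33 per 1000 for those at elevated risk, and it is tempting to apply that contrast here. The conditions it lists among the seizure cases are epilepsy, stroke, psychiatric disorders treated with threshold-lowering medication, tumors and arteriovenous malformation. It ties neither rate to family history or to implants.
- **A flaw in the low-risk rating.** In both risk passages that conclusion comes first and rests on the literature. The exclusions follow as an added precaution, and 19.1, which gives the overall rating, never mentions family history.
- **A threat to completing the trial.** Section 17.9 provides for suspension, not termination, and nothing shows that this mismatch makes a seizure materially more likely.
- **An undefined population.** Age, diagnosis, duration, pain level and the main exclusions are set out in section 7. Only a margin is ambiguous.

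**Conclusion.** The point holds as an internal inconsistency in the safety exclusions. The clear contradictions are family history of epilepsy (19.3 against 7.2 and 19.1) and implant scope (19.1 and 19.3 against 7.2), with ocular implants and devices near but outside the skull as the plain cases. Intrathecal pumps, spinal cord stimulators and past seizures without epilepsy are named only in 7.2.

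The size cannot be put as a number: the document does not say how many candidates would fall in the gap, and it gives no seizure rate for them. The conclusion rests on reading 7.2 as the operative list, which its wording and section 9.1 support, and on an ordinary reading of intracranial. It does not rest on any assumption about the questionnaire, and it makes no judgement on which exclusions are clinically right.

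**What to change.** Reconcile 7.2, 19.1 and 19.3 into one exclusion list. State it once in 7.2, and replace the lists in 19.1 and 19.3 with a cross-reference. For each item that differs (family history, past seizure without epilepsy, pregnancy, location and type of implant, spinal cord stimulators, intrathecal pumps) the investigators decide whether it applies and word it explicitly. Then check the phone screening document, the TMS questionnaire and the risk-factor form against the agreed list, and state which answers exclude.

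The cost is a wording amendment and a form check. If the wider exclusions are kept, there may be a few more screen failures.

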20.0 Potential Benefits to Subjects

20.1 Describe the potential benefits that individual subjects may experience by taking part in the research. Include the probability, magnitude, and duration of the potential benefits.

Based on the current literature it is expected that the rTMS and rehabilitation procedures used in this study will result in benefits such as reduced pain and increased function.¹⁻⁴ Subjects in the sham group will still receive high-quality rehabilitation that could lead to improved symptoms.

4. Moseley GL. Graded motor imagery for pathologic pain: A randomized controlled trial. *Neurology*. 2006;67(12):2129-2134. doi:10.1212/01.wnl.0000249112.56935.32

20.2 *Indicate if there is no direct benefit.*

NOTE: Compensation cannot be stated as a benefit.

N/A

Indicate if there is a potential benefit to others, future science or society.

N/A

